COPD	chronic obstructive pulmonary disease
COVID-19	coronavirus disease 2019
CRA	clinical research associate
CRF	case report form
CRO	contract research organization
CT	clinical trial
CTCAE	Common Terminology Criteria for Adverse Events
CYP	cytochrome P450
DILI	drug-induced liver injury

Abbreviation	Explanation
DLCO	diffusing capacity of the lungs for carbon monoxide
DNA	deoxyribonucleic acid
DSQ	Dysphagia Symptom Questionnaire
ECC	Emergency Contact Card
ECG	electrocardiogram
eCRF	electronic case report form
EDB	exposure during breastfeeding
EDP	exposure during pregnancy
eDiary	electronic diary
EEn	eosinophilic enteritis
EG	eosinophilic gastritis
EGD	esophagogastroduodenoscopy
eGFR	estimated glomerular filtration rate
EGID	eosinophilic gastrointestinal disease
EoE	eosinophilic esophagitis
EoE-HSS	Eosinophilic Esophagitis Histology Scoring System
EoE-QOL-A	Adult Eosinophilic Esophagitis Quality of Life
eos	eosinophils
EREFS	Eosinophilic Esophagitis Endoscopic Reference Score
ET	Early Termination
EudraCT	European Union Drug Regulating Authorities Clinical Trials Database
FA	fluorescein angiogram
FAQ	Food Avoidance Question
FAS	Full Analysis Set
FCS	fully conditional specification
FDA	Food and Drug Administration
FEV ₁	forced expiratory volume at 1 second
FSH	follicle-stimulating hormone
FVC	forced vital capacity
GCP	Good Clinical Practice
GERD	gastroesophageal reflux disease
GGT	gamma glutamyl transferase

Abbreviation	Explanation
GI	gastrointestinal
GWAS	genome-wide association studies
HBsAg	hepatitis B surface antigen
HBV	hepatitis B virus
HCV	hepatitis C virus
HIV	human immunodeficiency virus
hpf	high power field
HR	heart rate
HSS	Histology Scoring System
IAC	independent adjudication committee
IB	Investigator's Brochure
IC	informed consent
ICD	Informed Consent Document
ICF	informed consent form
ICH	International Council for Harmonisation of Technical Requirements for Pharmaceuticals for Human Use
IEC	Independent Ethics Committee
IgE	immunoglobulin E
IL	interleukin
IMID	immune-mediated inflammatory disorder
IND	Investigational New Drug
INR	international normalized ratio
IRB	Institutional Review Board
IUD	intrauterine device
IV	intravenous
IWRS	Interactive Web Response System
JAK	Janus kinase
LFT	liver function test
LS	least square
6-MP	6-mercaptopurine
MAR	missing at random
MedDRA	Medical Dictionary for Regulatory Activities
mFAS	modified Full Analysis Set

Abbreviation	Explanation
MI	multiple imputation
MMF	mycophenolate mofetil
MQI	Medically Qualified Individual
MTX	methotrexate
NASH	nonalcoholic steatohepatitis
OCT	optical coherence tomography
OIT	oral immunotherapy
PD	pharmacodynamic(s)
PEC	peak eosinophil count
PFT	pulmonary function test
PGIC	Patient Global Impression of Change
PGIS	Patient Global Impression of Severity
PHE	public health emergency
PK	pharmacokinetic(s)
PML	progressive multifocal leukoencephalopathy
PPI	proton pump inhibitor
PPI-REE	proton pump inhibitor-responsive esophageal eosinophilia
PRES	posterior reversible encephalopathy syndrome
PT	prothrombin time
PTEN	phosphatase and tensin homolog
qd	once daily
QOL	quality of life
QTcB	Bazett's corrected QT interval
QTcF	Fridericia's corrected QT interval
RNA	ribonucleic acid
S1P	sphingosine 1-phosphate
S1P _{1,4,5}	sphingosine 1-phosphate receptors 1, 4, 5
SAE	serious adverse event
SAM	severe atopy metabolic wasting
SAP	Statistical Analysis Plan
SCIT	subcutaneous immunotherapy
SD	standard deviation

Abbreviation	Explanation
SLIT	sublingual immunotherapy
SOP	standard operating procedure
SpO ₂	arterial oxygen saturation
SRSD	Single Reference Safety Document
6-TG	6-thioguanine
T bili	total bilirubin
TBNK	T, B, NK, CD4+ T cell and CD8+ T cell count (absolute number and percentage)
TEAE	treatment-emergent adverse event
TGF-β	transforming growth factor-beta
Th2	type 2 helper T
TNFα	tumor necrosis factor alpha
TSLP	thymic stromal lymphopietin
UC	ulcerative colitis
ULN	upper limit of normal
WBC	white blood cell
WOCBP	woman of child-bearing potential

1. INTRODUCTION

1.1. Background

1.1.1. Eosinophilic Esophagitis

Eosinophilic esophagitis (EoE) is a chronic and progressive, allergen-driven, immune-mediated disease of the esophagus. Histologically, EoE is characterized by the accumulation of eosinophils in the lining of the esophagus, a tissue that under normal conditions lacks these cells [2-4]. The presence of these unwelcome eosinophils has been shown to have a direct effect on immune function and tissue damage [3]. The eosinophilic predominant inflammation characteristic of EoE results in a variety of symptoms including but not limited to difficulty swallowing (dysphagia and/or odynophagia) and regurgitation, central chest pain, upper abdominal pain, food impaction, food refusal, and malnutrition [2,5,6]. Endoscopic abnormalities common to patients with EoE include esophageal linear furrows with loss of vascularity, trachealization, a small-caliber lumen, strictures, and mucosal exudates [2,3]. If left untreated, the natural course of disease ultimately progresses from chronic esophageal inflammation to fibrostenosis in the esophageal lining that increases tissue dysmotility and rigidity [7-9]. Spontaneous remission or development of tolerance to food allergies appears to be uncommon [9,10] and the disease commonly relapses in the absence of maintenance treatment [11-13]. Both pediatric and adult populations can develop EoE, however, the disorder is most common in individuals between the ages of 20 and 40 years old [14]. EoE also exhibits a strong heritability pattern and predominance for males and for Caucasians, and principally affects those in socioeconomically developed countries [3,8,14]. Risk factors for EoE include atopy and other allergic diseases, including asthma, allergic rhinitis, and atopic dermatitis [2,15].

Though the etiology of EoE is not yet completely understood, EoE is considered a type 2 helper T (Th2) cell-mediated atopic disease. EoE onset is thought to arise from a multifactorial interaction between genetic susceptibility and inappropriate immune-driven inflammatory responses to food antigens (predominantly non-immunoglobulin E [IgE]-mediated), aeroallergens, and environmental factors [2,5,16,17]. A genetic predisposition to disturbed barrier function, which is observed in esophageal tissue from EoE patients, permits allergenic molecules easy entry through the epithelium and subsequent Th2-driven allergic hypersensitivity [3,8,16]. Dendritic cells localized within the esophageal epithelium sample allergenic molecules and induce the activation and maturation of Th2 cells [4]. This Th2 cell-mediated activity leads to cytokine production (including interleukin [IL]-4, IL-5, and IL-13) and subsequent eosinophil activation and recruitment to the esophagus (eosinophilic inflammation) where the eosinophils release harmful secretory products that cause esophageal symptoms, further reinforcing the inflammatory cycle [3,8,18]. Thus, medical intervention that reduces esophageal inflammation, restores epithelial barrier integrity, and induces histologic remodeling can result in symptom improvement [7].

Genome-wide association studies (GWAS) have identified candidate genes involved in the pathogenesis of EoE including, but not limited to, thymic stromal lymphopoietin (*TSLP*) and calpain 14 (*CAPN14*), that when overexpressed can disrupt barrier integrity and increase allergic inflammation [5,8]. GWAS have also identified links between EoE and overexpression of eotaxin-3, an eosinophil-specific chemoattractant [3,17]. This genetic profile therefore supports an allergic etiology for EoE where a genetic predisposition enhances inappropriate immune responses to potential triggering events [8,16].

Diagnostic criteria currently required for the diagnosis of EoE include 1) symptoms of esophageal dysfunction; 2) eosinophilic esophageal inflammation with at least 15 eosinophils per high power field (hpf) affecting the esophagus alone; and 3) exclusion of other causes of esophageal eosinophilia. The other causes may include non-EoE eosinophilic gastrointestinal diseases (EGIDs) such as eosinophilic gastritis (EG) or eosinophilic enteritis (EEn), Crohn's disease (CD), infection, achalasia, and hypereosinophilic syndrome [6,9,16,19].

The differential diagnosis for EoE has historically included gastroesophageal reflux disease (GERD) and proton pump inhibitor (PPI)-responsive esophageal eosinophilia (PPI-REE), where responsiveness to an 8-week PPI study was considered an exclusion of an EoE diagnosis [5,6,20]. However, research suggested that EoE and GERD were not necessarily mutually exclusive and that PPIs may have an acid-independent anti-inflammatory effect that promotes the reduction of esophageal eosinophilia [5,6,21]. With the similarities in phenotypic, molecular, and pathophysiological characteristics and responses to treatment, PPI-REE emerged rather as a subtype of EoE in some patients. Based on these findings, PPI trial requirement was removed from the diagnostic algorithm [6] and PPIs are considered a treatment option, although off-label, for EoE.

Current treatment options for EoE may be dietary, pharmacologic, or endoscopic in nature. These treatments are subject to a variety of disadvantages including difficulty in adhering to dietary therapy, potential negative side effects associated with systemic corticosteroids, partial efficacy of topical steroids, and invasiveness and risks of endoscopic treatment, including esophageal dilation [7,21,22]. In 2018, budesonide was approved in Europe as orodispersible tablet formulation [23] for the treatment of EoE, but there are no Food and Drug Administration (FDA) approved medications for the treatment of EoE. Therefore, long-term safe and effective treatments are greatly needed.

Sphingosine 1-phosphate (S1P) receptor modulators have a primary mechanism of action of reducing peripheral lymphocytes. Given that immune system dysregulation is a pathophysiological feature of many immune-mediated inflammatory disorders (IMIDs) [24,25], synthetic small molecule S1P receptor modulators have the potential to act across a wide range of such diseases. S1P receptor modulators have been shown to reduce inflammation and induce clinical remission in multiple sclerosis (fingolimod, ozanimod, ponesimod, siponimod) [26-28], psoriasis (ponesimod) [29], and ulcerative colitis (UC [ozanimod, etrasimod]) [30,31]. Therefore, S1P receptor modulators, such as etrasimod, may have similar effects in EoE.

1.1.2. Etrasimod

Etrasimod (APD334) is an orally administered, synthetic, selective modulator of S1P receptors 1, 4, 5 (S1P_{1,4,5}) that is being developed to treat IMIDs.

S1P₁ is a cell surface expressed G protein-coupled receptor that has been shown to regulate lymphocyte migration out of lymphoid tissues. Synthetic small molecule S1P₁ agonists have been observed to act as functional antagonists by inducing sustained receptor internalization, thus inhibiting lymphocyte migration out of lymphoid tissues and lowering the amount of peripheral blood lymphocytes available to be recruited to sites of inflammation [32]. Nonclinical and clinical studies with S1P receptor modulators induce the anticipated S1P₁-mediated reduction in peripheral lymphocytes. Nonclinical studies of S1P receptor modulators have shown a reduction in tissue-infiltrating Th2 cells, cells expressing the pro-inflammatory cytokines IL-4,

IL-5, IL-13, and those cells implicated in active disease, including eosinophils [33-36]. In theory, a reduction in the number of circulating lymphocytes translates to reduced infiltration of inflammatory cells into the tissue and less release of pro-inflammatory cytokines which mediate tissue damage and eosinophil infiltration [32,37]. S1P receptor modulators have been shown to be clinically beneficial in other T cell mediated diseases including, but not limited to, inflammatory bowel disease, and multiple sclerosis [26,29,31,32]; etrasimod is therefore thought to be a potential therapeutic approach to the management of EoE.

Consistent with this hypothesis, etrasimod demonstrated positive results in a Phase 2, randomized, double-blind, placebo-controlled study in subjects with moderately to severely active UC in Study APD334-003 [38] and its open-label extension, Study APD334-005 [39]. Etrasimod significantly reduced circulating lymphocyte counts and demonstrated consistent and clinically meaningful improvements in endpoint measures reflecting cardinal symptoms of UC and objective findings of endoscopic colorectal mucosal healing [30,40-42]. Etrasimod 2 mg administered orally once daily for up to 46 weeks (per Amendment 2 of Study APD334-005 a subset of subjects received treatment for 52 weeks) was generally safe and well tolerated in subjects with UC.

A complete summary of the nonclinical and clinical data relevant to etrasimod and its study in human subjects is provided in the current edition of the Investigator's Brochure (IB).

1.2. Benefit-Risk Considerations

The need for a safe, long-term, oral, efficacious non-steroid treatment for EoE is illustrated by the lack of FDA approved medications for the treatment of EoE, and potential negative side effects or compliance difficulty associated with many currently available treatments.

The potential benefit to subjects who enroll in this study is clinical improvement in EoE symptoms as a result of reduced local inflammation in the esophagus through modulation of both T cell infiltration into the tissue and subsequent eosinophil accumulation (Section 1.1.2). As of 08 June 2020, etrasimod has been found to be generally safe and well-tolerated in approximately 736 adult subjects treated at various doses. The safety and tolerability of etrasimod has been evaluated in Phase 1 studies with healthy adult subjects at single doses up to 5 mg and repeated doses up to 2 mg once daily (qd) without dose-escalation and up to 4 mg qd with dose escalation. Etrasimod has previously demonstrated beneficial effects in another autoimmune inflammatory disease, UC. In a Phase 2 dose-ranging Study APD334-003, once daily treatment with 2 mg etrasimod for 12 weeks led to clinically meaningful and statistically significant endoscopic and symptomatic improvements versus placebo [38]. Sustained beneficial effects of etrasimod were observed for up to 46 weeks in the subsequent open-label extension Study APD334-005 (per Amendment 2 of Study APD334-005 a subset of subjects received treatment for 52 weeks) [39]. Although UC and EoE have different pathophysiology, they are Th2-driven immune-mediated inflammatory diseases where modulation of the S1P/S1P receptor axis is anticipated to provide therapeutic benefit to patients (Section 1.1.2). Therefore, it is reasonable to hypothesize that etrasimod may offer similar clinical benefits to EoE patients with active disease as UC patients. The clinical investigation proposed herein is necessary to affirm or reject this hypothesis.

While there have not been notable safety concerns with vital signs, electrocardiograms (ECGs), pulmonary function tests (PFTs), ophthalmoscopy, or laboratory test results with etrasimod, based on the mechanism of action of etrasimod and prior experience with S1P receptor

modulators such as fingolimod and siponimod in multiple sclerosis, monitoring for these specific safety parameters is planned for this study [43,44]. This monitoring includes PFTs, cardiac monitoring at first dose and on treatment re-initiation after a defined period of treatment interruption, liver function tests, and ophthalmoscopy with optical coherence tomography (OCT). Based on its mechanism of action, etrasimod is expected to dose-dependently reduce lymphocyte counts. This reduction is reversible, with lymphocyte counts returning to within normal limits following study drug discontinuation. Lymphocyte reduction may increase the risk of infections in some subjects. Thus, serial assessment of white blood cell (WBC) count and differential will be performed to assess the risk for serious and atypical infections and study subjects will be closely monitored by Investigators. Subjects with low lymphocyte count in circulation, or who have active infections will be excluded in this study.

S1P receptor modulators are associated with an expected, on-target, dose-dependent effect of reducing heart rate (HR) upon first dosing with HR recovery to predose baseline thereafter [45]. There have been no reported cases of symptomatic bradycardia on first dose, and rare first- or second-degree atrioventricular (AV) block found on ECG has been asymptomatic and transient (ie, spontaneous resolution) with etrasimod. An S1P₁-mediated HR reduction is maximal on the first day of dosing with etrasimod and typically peaks approximately 3 hours postdose on Day 1 with recovery thereafter. In Study APD334-003, the mean transient HR decrease did not exceed 10 beats per minute (bpm) on Day 1 up to 8 hours after dosing in all treatment groups, with the mean nadir of HR lowering for 2 mg etrasimod occurring 3 hours after dosing [38]. Therefore, a dose-escalation regimen is not necessary for doses up to 2 mg.

To protect vulnerable subjects, those with certain cardiac risks or pre-existing cardiac conditions (eg, recent myocardial infarction, cardiac conduction delay, recurrent symptomatic bradycardia or syncope) will be excluded from the study. Vital signs will be monitored closely during the study, and direct observation will be performed after the subject receives the first dose of etrasimod in each treatment period (at Day 1 [Double-Blind Treatment Period] and Week 24 [Extension Treatment Period]) or at treatment re-initiation after a defined period of treatment interruption (refer to Section 10.6.7.4 for additional information on Day 1 monitoring).

As additional safety measures, subjects with elevated liver enzymes, abnormal pulmonary function or pulmonary disease requiring hospitalization, and active retinopathy or macular edema will be excluded from the study.

Further description of identified risks, any potential risks, and the Reference Safety Information for etrasimod are provided in the current edition of the IB.

The safety profile of etrasimod coupled with a potent effect on the lymphocyte count demonstrate that etrasimod may be an effective oral treatment option for IMIDs such as EoE. Based on the favorable clinical safety and efficacy data that has been generated from etrasimod studies in healthy adults and subjects with UC, the precautions outlined above, and the current lack of safe and effective long-term oral medications for the treatment of EoE, the benefit/risk assessment justifies the further clinical development of etrasimod in subjects with EoE and the current Phase 2 study multi-center, randomized, double-blind, placebo-controlled study.

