 - e. Test positive for human immunodeficiency virus (HIV [positive HIV antibody]), hepatitis B virus (positive hepatitis B surface antigen [HBsAg]), or active hepatitis C (HCV [positive hepatitis C antibody with detectable HCV RNA]) at Screening

Note: If the Investigator suspects false positive hepatitis serology results, such as an antibody pattern indicating acute hepatitis infection, but no corresponding elevated liver enzymes and no signs or symptoms of liver disease, an infectious disease expert may be consulted. If the infectious disease expert finds no evidence of acute or chronic hepatitis infection and considers the serology results false positive and not clinically relevant, the Investigator may document (in source data and in the electronic case report form [eCRF]) that the serology results are considered false positive and may randomize the subject.

11. Have a serious infection that requires hospitalization or treatment with intravenous (IV) medications within 4 weeks prior to Baseline
12. Received a live-attenuated virus vaccine (except for recommended and age-appropriate influenza, measles/mumps/rubella, or varicella vaccine) within 4 weeks prior to Baseline
13. History of malignancy of any organ system (other than localized squamous cell or basal cell carcinoma of the skin that have been excised or resolved), treated or untreated, within the past 5 years regardless of whether there is evidence of local recurrence or metastases
14. Have active epilepsy
15. Have a history of cirrhosis
16. Have any of the following conditions or receiving treatments that may affect cardiovascular function:
 - a. Myocardial infarction, unstable angina, stroke/transient ischemic attack, decompensated heart failure requiring hospitalization or Class III/IV heart failure within 8 weeks prior to Baseline
 - b. Second-degree or third-degree AV block, sick sinus syndrome without a functional pacemaker, or periods of asystole for > 3 seconds without an implanted cardiac pacemaker
 - c. Recurrent symptomatic bradycardia or recurrent cardiogenic syncope
 - d. Confirmed Screening and Day 1 baseline vital signs (taken in the sitting position) with a HR < 50 bpm OR systolic blood pressure (BP) < 90 mm Hg OR diastolic BP < 55 mm Hg.
 - e. Confirmed Screening and Day 1 baseline ECG with PR interval \geq 200 ms or Friderica's corrected QT interval (QTcF) \geq 450 ms in males or \geq 470 ms in females.
 - f. Receiving Class Ia or Class III anti-arrhythmic drugs

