 - g. Start, stop, or change dosage of Class Ib, II, or IV anti-arrhythmic drugs within 1 week prior to Baseline
17. Have active diabetic retinopathy, uveitis, retinitis pigmentosum, macular edema, or had an intraocular surgery within 12 months prior to Baseline. Refer to [Appendix 11](#) for modification in the event that coronavirus disease 2019 (COVID-19) or similar public health emergency (PHE)-related restrictions limit the capacity to perform non-essential ophthalmoscopy with OCT.
18. Have a confirmed forced expiratory volume at 1 second (FEV₁) or forced vital capacity (FVC) of < 70% predicted (prior to the administration of a short-acting bronchodilator) on Screening PFTs. Refer to [Appendix 11](#) for modification in the event that COVID-19 or similar PHE-related restrictions limit the capacity to perform non-essential PFTs.

Exclusion criteria related to test or laboratory results (performed by central laboratory)

19. Have confirmed absolute lymphocyte count (ALC) < 0.8×10^9 cells/L at Screening
20. Have confirmed aspartate aminotransferase (AST) or alanine aminotransferase (ALT) > 2 \times upper limit of normal (ULN) and total bilirubin > 1.5 \times ULN (unless consistent with a history of Gilbert's Syndrome) at Screening

21. Have confirmed moderate or severe renal impairment (estimated glomerular filtration rate [eGFR] < 60 mL/min/m²)

General exclusionary criteria

22. Lactating female who is breastfeeding
23. Females who are pregnant, evidenced by a positive serum beta-human chorionic gonadotropin (β -hCG) pregnancy test at Screening and/or urine dipstick pregnancy test at Day 1, or females who do not meet criterion a or agree with criterion b below, or males who do not agree with criterion c below
- a. A female who is not of child-bearing potential must meet 1 of the following:
- Postmenopausal, defined as no menses for 12 months without an alternative medical cause and confirmed by follicle-stimulating hormone (FSH) within postmenopausal range according to local standards
 - Had permanent sterilization procedure, such as hysterectomy, bilateral salpingectomy, or bilateral oophorectomy

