- b. A female who is of child-bearing potential must agree to using a highly effective contraception method during treatment and for 4 weeks following treatment that can achieve a failure rate of less than 1% per year when used consistently and correctly. The following are considered highly effective birth control methods: Combined (estrogen and progestogen containing) hormonal contraception associated with inhibition of ovulation, which may be oral, intravaginal, or transdermal; progestogen-only hormonal contraception associated with inhibition of ovulation, which may be oral, injected, or implanted; intrauterine device (IUD); intrauterine hormone-releasing system; bilateral tubal occlusion; vasectomized partner; sexual abstinence (complete sexual abstinence defined as refraining from heterosexual intercourse for the entire period of risk associated with study treatments). The reliability of sexual abstinence needs to be evaluated in relation to the duration of the clinical study and the preferred and usual lifestyle of the subject. Periodic abstinence (eg, calendar, symptothermal, or post-ovulation methods) is not acceptable
- c. A male with pregnant or non-pregnant woman of child-bearing potential (WOCBP) partner must agree to use condoms during treatment and for 4 weeks following the last dose of study treatment
24. Any acute illness or medical condition including cognitive impairment and alcohol/drug abuse/dependence, or signs/symptoms suspicious for a serious disease that, in the Investigator's opinion, could put the subject at increased risk for safety event(s), confound interpretation of study results, or interfere with the subject's ability to comply with protocol-specified procedures or assessments.

Testing positive for COVID-19 is NOT exclusionary on its own if other exclusion criteria (#11 or #24) are not met. If a subject screen fails due to COVID-19, the subject may be re-screened for the study when their COVID-19 symptoms have improved or resolved but no sooner than 10 days after the first date of COVID-19 symptom onset. Subjects who are asymptomatic after COVID-19 recovery are not required to show a negative COVID-19 viral or serology test in order to qualify for re-screening.

For subjects who have not received the COVID-19 vaccine, it is recommended that COVID-19 vaccination is completed 14 days prior to randomization.

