9.2. Screening

Subjects must sign the informed consent form (ICF) and meet study eligibility criteria before any study-specific procedure can be performed ([Section 12.2](#)).

All screening evaluations should be completed and reviewed within 35 days prior to Day 1 to confirm subject eligibility. In some cases, the screening visit window for a given subject may be extended by 2 business days beyond the date the Investigator receives the screening histopathology report to confirm subject eligibility. Note that only extension of the screening visit window due to a legitimate delay in the reporting of screening histopathology report will be approved by the Medical Monitor and will not be considered a protocol deviation.

Refer to [Appendix 11](#) for modification in the event that COVID-19 or similar PHE-related restrictions limit the capacity to perform certain Screening assessments.

The Medical Monitor should be consulted to see whether repeat testing is needed if the subject is planned to be enrolled > 35 days from the signing of the ICF.

The Screening EGD should be performed early in the screening period (preferably within the first 7 days of the screening period) to allow sufficient time for central reading to confirm eligibility by histology.

During Screening, subjects will record daily presence of dysphagia to solid food in their eDiary, according to the question-answer format of the DSQ. Subjects will begin daily eDiary entries starting on the first day of Screening after the eDiary training is completed. eDiary device and training should be provided at Screening to ensure capturing of entries within the required 14-day period. Study site staff will monitor the eDiary compliance. At least 8 DSQ daily entries in the last 2 weeks prior to Day 1 visit as well as completion of Patient Global Impression of Severity (PGIS) are needed for randomization.

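### Section 1.2 says subjects with pulmonary disease requiring hospitalization will be excluded, but Section 4.2 has no such criterion; the clause exists only as an optional Appendix 11 change when Screening PFTs cannot be performed

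*Protocol*

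**What the plan says.** Protocol Section 1.2 lists subjects to be kept out of the study as additional safety measures. Among them are those with "abnormal pulmonary function or pulmonary disease requiring hospitalization". No time limit or condition is attached. Slightly earlier the section says: "Subjects with low lymphocyte count in circulation, or who have active infections will be excluded in this study". Its closing benefit-risk statement rests on three grounds: existing safety and efficacy data, "the precautions outlined above", and the shortage of long-term oral treatments for EoE.

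Section 4.2 sets eligibility:

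- No. 18 begins "Have a confirmed forced expiratory volume at 1 second" and excludes on FEV1 or FVC below 70% predicted at Screening. It does not mention hospital admission.
- No. 11 reads "Have a serious infection that requires hospitalization or treatment with intravenous (IV) medications within 4 weeks prior to Baseline".
- No. 24 begins "Any acute illness or medical condition including cognitive impairment and alcohol/drug abuse/dependence". It applies when the investigator judges that the condition raises safety risk, confounds the results or interferes with compliance.

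Appendix 11 (Safety Assessments, item 3) allows no. 18 to be changed when Screening PFTs cannot be performed. The changed text adds a pulse-oximetry limit (SpO2 of 92% or less on room air) and a lung-disease admission 6 months or less before Baseline.

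**The concern.** Section 1.2 gives two lung-related grounds, joined by an 'or': abnormal function, and disease that led to admission. Only the first became a standing criterion. The second applies only when spirometry is unavailable, and even then at the sponsor's option. A subject described as excluded in the benefit-risk section can therefore be eligible under the section that governs entry.

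The stake is subject protection and the accuracy of the benefit-risk statement. Section 10.6.7.5 says pulmonary function is assessed because of changes seen with other S1P receptor modulators, and Section 10.6.8.1.4 lists pulmonary events as potential events of special interest. As written, dosing a recently admitted subject with passing PFTs depends largely on how each investigator uses no. 24.

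**Working it through.** The plan gives no figure to reproduce. The main check sets each exclusion stated in Section 1.2 against Section 4.2.

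| Exclusion stated in Section 1.2 | Standing criterion in Section 4.2 | Fixed criterion? |
|---|---|---|
| Certain cardiac risks or conditions | No. 16 | Yes |
| Active retinopathy or macular edema | No. 17 | Yes |
| Abnormal pulmonary function | No. 18 (FEV1 or FVC < 70% predicted) | Yes |
| Low lymphocyte count | No. 19 (confirmed ALC < 0.8 × 10^9 cells/L) | Yes |
| Elevated liver enzymes | No. 20 | Yes |
| Active infection | 1a, 10c, 10d, 10e and 11; the rest through no. 24 | In part |
| Pulmonary disease requiring hospitalization | None | No |

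**Pulmonary admission, PFTs done and passing.** The routes to exclusion are:

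1. No. 18 does not apply, since FEV1 and FVC pass.
2. The Appendix 11 clause does not apply, since its trigger (PFTs cannot be performed) is absent.
3. No. 11 applies only to a serious infection within 4 weeks before Baseline.
4. 10c applies only to an opportunistic infection, with no time limit; it names pneumocystis pneumonia.
5. Otherwise, for example after an asthma admission, no. 24 decides.

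**Active infection.** The fixed criteria cover esophageal infection (1a), history of opportunistic infection (10c), history of disseminated herpes (10d), HIV, hepatitis B and active hepatitis C (10e), and serious infection (no. 11). Other infections fall to no. 24. The COVID-19 paragraph in Section 4.2 confirms this routing: a positive test alone does not exclude unless no. 11 or no. 24 is met. Eligibility is confirmed again on Day 1 (Table 7 marks the row at W0/D1, and Section 9.3.2 randomizes only afterwards). Here the wording of Section 1.2 is broader than the criteria, but the criteria are coherent.

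**Cost of a standing 6-month clause.** Section 10.3.7 lets EGD, OCT and PFT results be reused if obtained within 90 days before Day 1. Section 9.2 asks for the EGD "preferably within the first 7 days of the screening period", that is, Day -35 to Day -29.

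- Delay possible without a repeat EGD, counted from the planned Day 1: 90 - 35 = 55 days to 90 - 29 = 61 days.
- Longest wait for a 6-month look-back to run out: 181 to 184 days, if the admission was just before the planned Day 1.
- Reuse therefore suffices only if the admission was at least 181 - 61 = 120 to 184 - 55 = 129 days before the planned Day 1, depending on the EGD date and the calendar. After a more recent admission, a later entry would need a repeat EGD.

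**The case against.** The strongest reply is that Section 1.2 is a summary and uses shorthand throughout: a low lymphocyte count becomes an ALC limit, and abnormal pulmonary function becomes a spirometric limit. On this view the Appendix 11 clause merely replaces spirometry that cannot be done, so requiring it when spirometry passes is a new design choice. No. 24 is a binding criterion, and the investigator is well informed when applying it. Section 10.6.5 collects respiratory history at Screening and conditions affecting the PFT before each test, and Section 10.3.4 records the reason and year of every hospitalization. Rewording Section 1.2 would remove the mismatch by itself.

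Part of this stands. Section 1.2 gives no look-back, so the 6 months is the sponsor's figure from another setting. No. 24 does allow exclusion. Rewording would restore consistency, but only by giving up a protection that the benefit-risk section claims. The shorthand argument does not reach the pulmonary clause: the other phrases were each turned into a criterion, and this one was not. Nor does Section 1.2 make the admission ground depend on missing PFTs.

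Three stronger readings are not supported:

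- **That actively infected subjects enter unchecked.** No. 24 covers acute illness and is checked again on Day 1. The Day 1 white cell count should not be cited as part of that check, however. Table 3 note a has investigators assess it, but Section 9.3.1 has the blood drawn on Day 1 itself, Section 9.1 sends it to a central laboratory, and Table 7 note l requires only the Screening results to be reviewed before the first dose.
- **That every recent pulmonary admission rests on no. 24 alone.** Nos. 11 and 10c catch some, and no. 18 catches those whose lung function is still below the limit.
- **That the 4 weeks in no. 11, set against 6 months, measure the share left uncovered.** That ratio counts calendar days in a window taken from Appendix 11. It is neither a share of subjects nor a measure of risk.

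**Conclusion.** The point holds for pulmonary admission. Section 1.2 states the exclusion without condition, and Section 4.2 does not contain it. For active infection the mismatch is one of wording, because leaving the remaining non-serious infections to no. 24 appears deliberate.

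The size is limited. The documents give no rate of recent pulmonary admission among candidates, so the number of subjects affected is unknown. The precautions are one of three grounds for the benefit-risk conclusion, so a reader should not infer that the conclusion fails. No endpoint, analysis or statistical figure changes, and no effect on event rates is claimed.

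The recommendation assumes that the sponsor intended the admission exclusion as Section 1.2 states it, and that its own 6-month figure is a reasonable look-back.

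**What to change.** 1. **No. 18.** Make the Appendix 11 clause (lung-disease admission 6 months or less before Baseline) an unconditional part of the criterion. Check it from the history or source records; Section 14.1.2 already counts hospital records as source documents. Record the month of admission as well as the year, because a year alone cannot settle a 6-month look-back.
2. **Section 1.2, infection sentence.** Reword it to match 1a, 10c to 10e, 11 and 24: named infections, serious infections, and acute infections that the investigator judges to raise risk.
3. **Optional.** A fixed deferral for clinically significant active infection may be added beside no. 11. It must exempt or cross-reference the COVID-19 paragraph; otherwise a COVID-19 subject on an oral antiviral would fall under conflicting rules.

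The cost is one criterion, one date field and a wording change in an amendment, with no new test. The downside is some screen failures, probably few but not quantifiable from the documents. Asthma admissions are a possible source, since Section 1.1.1 lists asthma as a risk factor for EoE. A later attempt needs new consent and a new Screening Period (Section 10.3.7), with at least 8 DSQ entries in the last 2 weeks (Section 9.2). Some subjects would need EGD, OCT and PFT repeated beyond the 90-day limit. Taking the admission history before the Screening EGD would avoid part of that.

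The documents do not state enrollment status. If enrollment has closed, only the alignment of Section 1.2, including its pulmonary clause, remains useful.
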